7 STATISTICAL METHODS OF ANALYSIS

7.1 General Principles

All tables, figures, listings and inference analyses will be produced using Stata-files (Stata12.1 [REDACTED] USA).

7.1.1 Standards:

- All tables and figures other than dosimetry and PK will be grouped by subjects' disease (RA/AS), and will also include a total column for all patients receiving Annexin. Dosimetry and PK tables and figures will only include the total of patients in the PK/dosimetry population (not separated by disease group).
- Summary tables and listings will use Courier New font of size 9 with a default page orientation of landscape.
- The code is made of 5 digits, resulting from the combination of the site identification letter "SW" and the subject number.
- Any CRF data, third party electronic data (such as clinical laboratory data) as well as any corresponding derived variable listed will be presented sorted by subject unless otherwise specified.
- Flags for abnormal laboratory parameters will be displayed in the individual subject data listings. For the classification of abnormal laboratory values, the individual normal and safety ranges of the central laboratory will be used and will be displayed in the listings.
- Categorical variables will be presented using number of subjects in the analysis population (N), number of subjects with non-missing observations (n), and frequency and percentages by category. Denominators for calculation of percentages will be taken as the number of subjects with non-missing observations (n) in the specified population unless otherwise stated.
- Continuous variables will be presented using number of subjects in the analysis population (N), number of subjects with non-missing observations (n), mean, standard deviation (abbreviated as "SD" in statistical tables), median, quartiles, minimum and maximum.
- All hypothesis testing will be considered exploratory. Unless stated otherwise, statistical tests conducted will be two-sided at a level of $p=0.05$, although care will be taken to avoid over-emphasis on nominal significance levels. No adjustments for multiplicity issues will be made in this study.

- Dates will be presented as DDMMYYYY.
- Times will be presented in hours and minutes using a 24 hour clock (i.e. hh:mm).
- Numeric values will be decimal point aligned.
- Character values will be left aligned.
- The tables, listings and figures will be delivered in a RTF format.

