## **2 STUDY OBJECTIVES AND HYPOTHESIS**

This Phase I-IIa study will be undertaken to determine the safety, tolerability, biodistribution and ability of early imaging with 99mTc-rhAnnexin V-128 to predict response to treatment. Patients with diagnosed rheumatoid arthritis (10 patients) or ankylosing spondylitis (10 patients) will be imaged on Day 1 and after a suitable interval time (6 weeks +/- two weeks) post-first administration of the imaging product.

Ten patients, independently from the group (RA or AS), will participate to a dosimetry and PK sub-study after written approved consent. These patients will have additional images and blood sampling at Day 1 and 24 hrs after administration of 99mTc-rhAnnexin V128. In these patients urines will be also analysed as a function of time by SEC-HPLC.

Out of the first 6 patients, at least 3 patients must be enrolled in the dosimetric and PK sub-study.

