#### **Secondary Objectives:**

- To determine the biodistribution, pharmacokinetics and radiation dosimetry of 99mTc-rhAnnexin V-128
- To demonstrate the time-dependent distribution and localization of 99mTc-rhAnnexin V-128 both in RA and AS patients
- To determine ability of early imaging with 99mTc-rhAnnexin V-128 to evaluate the presence of lesions before and after short term treatment of either RA or AS patients

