### **Details on treatment of the patients:**

Patients with RA will be diagnosed based on ACR/EULAR10 and will thereafter be evaluated with DAS 28. Patients with AS will be diagnosed based on the ASAS criteria. Each patient will be anonymized and identified with a patient ID number.

A unique subject identification number (Patient ID) will be assigned at the start of the Screening Period to each subject who signs the informed consent form until the study termination of the patient. This number will identify the subject throughout the study.

Patient IDs will include the 2-digit country code number (SW) and a 3-digit subject number (ex: SW001 for first subject In).

In both groups of patients – i.e. RA and AS patients – the introduction of a Bi-DMARD treatment should be indicated at the moment of inclusion in the study. The Bi-DMARD therapy should start on Day 2 of the study. RA patients must have been treated at least with one DMARD (methotrexate, leflunomide and sulfasalazine) or a combination of them in the last 3 months – before inclusion - and this/these DMARD(s) will be continued in this study. Otherwise, RA patients must have been previously treated with Bi-DMARD before administration of the new Bi-DMARD treatment. The non-response of the previous Bi-DMARD treatment must be documented.

AS patients must at least have been treated with NSAID in the last 3 months before inclusion and they

should be under the same NSAID treatment during the last 4 weeks before inclusion.

For RA patients, anti-tumour necrosis factor (TNF) antibodies, anti-interleukine 6 (IL-6) antibodies and abatacept therapies are to be considered and are authorized in Switzerland as first line Bi-DMARD agents in RA. On the contrary, anti-CD 20 positive lymphocytes antibodies can only be used, if one anti-TNF therapy failed.

In the AS patients group, only anti-TNF antibodies can be considered, if NSAID are not sufficient.

Ten patients enrolled in the study will be asked to participate in a dosimetry and PK sub-study, irrespective of the group they are part of (RA or AS).

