### **Sample size**

The number of patients in this study is not based on statistical power considerations. The planned sample includes 20 patients with Day 56 assessments which are believed to provide sufficient data to assess the general safety and tolerability of 99mTc-rhAnnexin V-128. Patients will be recruited with a ratio of 1:1 RA:AS.

Any patient who has not completed Day 56 assessment will be replaced by a patient from the same group (RA or AS). It is expected that about 10% of patients will not complete their Day 56 assessments; therefore, approximately 23 patients will be recruited.

In addition, 10 patients enrolled in the study will be asked to participate in a dosimetry and PK study, irrespective of the group they are part of (RA or AS).

Out of the first 6 patients, at least 3 patients must take part in the dosimetric and PK sub-study.

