3 STUDY OBJECTIVES

This Phase I-IIa study will be undertaken to determine the safety, tolerability, bio-distribution and ability of early imaging with $99mTc$ -rhAnnexin V-128 to predict response to treatment in 20 patients with diagnosed rheumatoid arthritis (RA) or ankylosing spondylitis (AS).

The objectives of this study are:

- To determine the safety and tolerability of imaging with $99mTc$ -rhAnnexin V-128.
- To determine the biodistribution, pharmacokinetics and radiation dosimetry of $99mTc$ -rhAnnexin V-128
- To demonstrate the time-dependent distribution and localization of $99mTc$ -rhAnnexin V-128 both in RA and AS patients
- To determine ability of early imaging with $99mTc$ -rhAnnexin V-128 to evaluate the presence of lesions before and after short term treatment of either RA or AS patients

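### Time-dependent distribution is an objective in both RA and AS, but the SAP plans no by-disease report of the serial imaging

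*SAP*

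**What the plan says.** **Objective.** Protocol Section 2 lists as a secondary objective "To demonstrate the time-dependent distribution and localization of" the tracer, and SAP Section 3 repeats it, ending with "both in RA and AS patients". Biodistribution, pharmacokinetics and dosimetry form a separate secondary objective that names no disease.

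**Sub-study.** Protocol Section 2: "Ten patients, independently from the group (RA or AS), will participate to a dosimetry and PK sub-study after written approved consent". The note to Figure 1 in SAP 4.1 makes ten the upper limit. The only minimum is in Protocol Section 8, Sample size: "Out of the first 6 patients, at least 3 patients must take part in the dosimetric and PK sub-study". It is not set by disease. The balance rule, "Patients will be recruited with a ratio of 1:1 RA:AS", applies to the main study.

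**Reporting.** SAP 7.1.1 groups all other tables and figures by RA and AS with a total column, then makes one exception: "Dosimetry and PK tables and figures will only include the total of patients in the PK/dosimetry population (not separated by disease group". SAP 7.14, headed Pharmacokinetics and Dosimetry, is where whole-body planar biodistribution is placed.

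**Lesion analysis.** SAP 6.5 and 7.17 plan a separate description of lesion number, location and intensity at each imaging time. SAP 6.5 limits it to patients with 1 h and 2 h images at both Day 1 and Day 42. SAP 7.17 gives the work to the sponsor's study physician, with results appended to the study report.

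**The concern.** The objective that names both diseases is also the one about change over time. The only patients with a full time course are those whose results the SAP says to pool. The grouping by disease that applies to the other outputs is thus dropped where this objective would need it.

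If nothing changes, the planned summaries will give at most one mixed description of distribution over time. A reader of the study report would not be told how many patients of each disease lie behind it, or whether the two diseases look alike. I found no protocol text that requires the pooling; Section 8, Dosimetry, asks only for descriptive statistics.

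SAP 4.2 promises a data review before the SAP is finalized, to judge which secondary analyses remain worth doing. I found no outcome of that review in the SAP, and SAP 7.19 reports no changes to the planned analysis.

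**Working it through.** The plan gives no figure on this point. Its only sizing figure, about 23 recruited for 20 evaluable with 10% loss, reproduces: 20 / (1 − 0.10) = 22.2, rounded up to 23. Nothing below changes it.

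**Step 1. Who has a time course** (Protocol Table 1 note 5; Section 6, Dosimetry)

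| Patients | Image times after the first injection |
|---|---|
| First 3 in the sub-study | 30 min, 60 min, 2 h, 4 h, 24 h |
| Next 7 in the sub-study | the same, or 3 h for 2 h and 6 h for 4 h |
| First 3 outside the sub-study | 60 min and 2 h |
| Later patients outside it | a time chosen from the first 3 sub-study patients |

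Only the sub-study spans 30 min to 24 h.

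**Step 2. Which reporting rule applies.** Whole-body biodistribution sits in SAP 7.14, so it falls under the total-only rule. The lesion analysis in SAP 6.5 and 7.17 is neither PK nor dosimetry, so it falls under the RA/AS rule.

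**Step 3. What is planned.** Tables 14.2.1 to 14.2.6 and Figures 14.2.1 to 14.2.6 cover blood, serum and urine. None shows whole-body or organ activity against time, pooled or by disease. SAP 10.1 has no scintigraphy table. Listing 16.2.4.18 covers whole-body planar imaging by subject.

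**Step 4. How uneven the sub-study could be.** Assume 10 sub-study patients drawn at random from 10 RA and 10 AS. Then P(k RA) = C(10,k)² / C(20,10) = C(10,k)² / 184,756.
- One disease supplies 3 or fewer: 2 × (1 + 100 + 2,025 + 14,400) / 184,756 = 17.9%.
- One disease supplies 2 or fewer: 2 × (1 + 100 + 2,025) / 184,756 = 2.3%.
- One disease absent: 2 / 184,756 = about 0.001%.
- At least 4 of each: 100 − 17.9 = 82.1%.

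Sensitivity, all on assumed inputs:
- SAP 4.2 speaks of at least 80% of the planned 20, which is 16. Taken as 8 + 8 with 10 in the sub-study, 3 or fewer has 11.9% and 2 or fewer 0.7%. With 8 in the sub-study, 2 or fewer has 13.2%.
- If each of 10 entrants has a 70% chance of coming from one disease (binomial), 2 or fewer of the other has 38%. At 80% it is 68%.

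The documents do not give the actual split.

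**Step 5. What by-disease means could show.** The 95% CI half-width in SD units is t(0.975, n−1) / √n.
- n = 10: 2.262 / 3.162 = 0.72
- n = 5: 2.776 / 2.236 = 1.24
- n = 4: 3.182 / 2 = 1.59
- n = 3: 4.303 / 1.732 = 2.48

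**The case against.** The strongest case for the plan has five parts.

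- **The pooling rule serves a different objective.** PK, biodistribution and dosimetry have their own objective, which names no disease. This stands for blood and urine: nothing in the objective at issue asks for those curves by disease. It does not stand for the images, because the same serial images are the only full record of distribution over time.
- **Localization is covered by disease.** The lesion analysis falls under the RA/AS rule. This stands in part. It describes lesions, not whole-body or organ distribution, and assures only 1 h and 2 h. Its eligible group may be small: the protocol fixes no 1 h and 2 h pair at Day 42, and 2 h may become 3 h in the sub-study.
- **Listings keep the data.** With about 10 patients, subject listings can be matched to diagnosis. That is so, but a listing whose content is not specified is no planned summary. The separate PK/immunology plan announced in Protocol Section 8 is not among the documents and cannot be judged.
- **The objective may mean one population containing both diseases.** The wording allows this. The SAP does not say that this reading was chosen.
- **The numbers are too small for comparison.** This stands, and it limits any by-disease display to description.

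A reader might go further and infer that the objective cannot be answered by disease at all. The documents do not support that. Part of the localization question has a by-disease analysis, individual data are retained, and under random entry both diseases supply at least 4 patients in about 82% of draws. A split of 10 to 0 is possible under the rules, but nothing shows that it is likely.

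**Conclusion.** The concern holds as a reporting gap. The planned outputs contain no summary of the whole-body or organ time course by disease, and the sub-study rules guarantee no particular number from either disease. The time-course part of the objective will therefore not be reported for RA and AS separately as planned.

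The gap is modest. It removes no data and does not touch the primary safety objective. The imbalance figures rest on random entry from equal groups; entry by consent could be more uneven. The precision figures assume roughly normal data. They show that separate disease means would be imprecise, so neither a test nor a claim of difference or similarity would be justified.

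A reader might also infer that the protocol should set a minimum per disease for the sub-study. That remedy is no longer open: SAP 4.2 records the decision to stop recruitment by the end of September 2017, and the SAP's revision history is dated 26 January 2018.

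**What to change.** Change the SAP only.

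1. In 7.1.1, exempt the serial biodistribution displays from the total-only rule. Leave the rule in place for blood, serum and urine.
2. In 7.14 and the lists in Section 10, add a table of whole-body and organ percent injected activity by time point, with RA, AS and Total columns and the n per disease. Add a figure of individual curves coded by disease.
3. Label both as descriptive, with no test between diseases.
4. If the sponsor meant one mixed population, say so in SAP Section 3, so that a pooled result is read as intended.

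This is a free improvement. It needs no further patients, visits or measurements, and the Total column keeps the pooled result. The cost is one table shell and one figure shell. The drawback is that small by-disease columns may be over-read, which the descriptive label and the stated n are meant to prevent.

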7.1.2 Handling of Missing Data and Data from Unscheduled or Repeat Visits

No imputations of missing data will be used in the analysis of safety data and PK/Dosimetry. In particular for PK, a minimum number of 3 valid time points is required for including the subject in the PK analysis.

For summary statistics, only data from scheduled visits will be used. Data from unscheduled visits or repeat tests will not be used when descriptive statistics are presented by visit. However, all observed data including repeat tests and unscheduled visits will be presented in assessments of max and min changes on treatment, shift tables and in listings. Missing data will appear as blank.

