7.9 Safety Laboratory Evaluation

Summary statistics (n, mean, SD, median, quartiles, minimum, maximum) will be presented at each assessment time point for each continuous laboratory assessment, including routine haematology, chemistry and urinary panels. Summary statistics changes from baseline will also be presented. For categorical variables the outputs will be generated according to the section 7.1.1.

For the classification of abnormal laboratory values, the individual normal range of the laboratory will be used.

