7.11 Vital Signs

Summary statistics (n, mean, SD, median, quartiles, minimum, maximum) of vital signs will be presented at each assessment time point. Summary statistics of changes from baseline will also be presented.

Number and percentage of subjects with shift changes from baseline will be tabulated in Shift Tables for each vital sign assessment.

The following normal ranges for vital signs will be used:

Systolic blood pressure	BETWEEN 90 AND 150 (mm Hg)
Diastolic blood pressure	BETWEEN 45 AND 90 (mm Hg)
Heart Rate	BETWEEN 40 AND 100 (beats/min)

Listings of all vital signs will be presented.

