10 APPENDICES

10.1 List of tables

Number	Table Title	Analysis set
14.1.1	Subject Disposition	Screened
14.1.2	Summary of Protocol Deviations	Safety
14.1.3	Demographics and Baseline Characteristics	Safety
14.1.4	Medical History	Safety
14.1.5	Prior Medications	Safety
14.1.6	Concomitant Medications	Safety
14.1.7	Extent of Exposure: Summary of injected Dose of the investigated imaging product.	Safety
14.2.1	Blood and serum concentrations of total radioactivity	PK
14.2.2	Blood and serum area under the concentration-time curve (AUC) and terminal half-life (t _{1/2}) of total radioactivity after intravenous 99mTc-rhAnnexin V-128	PK
14.2.3	Summary of Percent excretion of total radioactivity in urine	PK
14.2.4	Summary of Serum concentrations of rhAnnexin V-128 based on ELISA analysis	PK
14.2.5	Summary of Volume of distribution (V _z) and systemic clearance (Cl) of rhAnnexin V-128 based on ELISA analysis	PK
14.2.6	Summary of SEC-HPLC analysis results	PK
14.3.1.1	Overall Summary of TEAEs	Safety
14.3.1.2	Occurrence of TEAEs – Number and percentage of subjects by System Organ Class and Preferred Term	Safety
14.3.1.3	Occurrence of Serious TEAEs – Number and percentage of subject by System Organ Class and Preferred Term	Safety
14.3.1.4	Occurrence of TEAEs Leading to permanent treatment discontinuation – Number and percentage of subject by System Organ Class and Preferred Term	Safety
14.3.1.5	Occurrence of Serious TEAEs Severity – Number and percentage of subject by System Organ Class and Preferred Term	Safety
14.3.1.6	Occurrence of Serious TEAEs Relationship to study drugs – Number and Percentage of Subjects by System Organ Class, and Preferred Term	Safety

Number	Table Title	Analysis set
14.3.1.7	Occurrence of TEAEs Relationship to study drugs – Number and Percentage of Subjects by System Organ Class, and Preferred Term	Safety
14.3.1.8	Occurrence of TEAEs Severity – Number and Percentage of Subject by System Organ Class and Preferred Term	Safety
14.3.2	Listing of Deaths and Other Serious Adverse Events	Safety
14.3.4.1	Listing of Laboratory Safety Values for Subjects with Clinically Significant Abnormal Laboratory Values	Safety
14.3.4.2	Haematology parameters at each visit and change from baseline	Safety
14.3.4.3	Biochemistry parameters at each visit and change from baseline	Safety
14.3.4.4	Urinalysis parameters at each visit and change from baseline	Safety

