14.3.5	Disease Assessment (BASDAI, BASFI, BASMI, DAS28, ACR/EULAR scores) at each visit and change from baseline	Safety
14.3.6	Listing of Anti-Annexin V-128 IgG and IgM antibodies Reactive results	Safety
14.3.7	Physical examination at each visit	Safety
14.3.8.1	Vital signs at each visit and change from baseline	Safety
14.3.8.2	Vital signs – Shifts from baseline	Safety
14.3.9.1	Overall Electrocardiogram interpretation	Safety
14.3.9.2	Electrocardiogram parameters at each visit and change from baseline	Safety

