Data source: listings 16.x.x.x.x and 16.x.x.x.x.

Source code: xxxx.ssc. Date/time of run: DDMMYYYY:HH:MM.

Physical examination includes: height, weight, BMI

Page X of Y

STA01form01v3

Advanced Accelerator Applications
 Protocol: AAA-1002

Table 14.3.8.1 Vital Signs at each visit and change from baseline
 Population: Safety

Test (unit)	Visit	Statistic	RA (N=xx)		AS (N=xx)		V-128 Total (N=xx)	
			Raw	Change from Baseline	Raw	Change from Baseline	Raw	Change from Baseline
Systolic Blood Pressure Supine (xx/yy)	Baseline[1]	n	XXX		XXX		XXX	
		Mean	XXX.XX		XXX.XX		XXX.XX	
		SD	XXX.XXX		XXX.XXX		XXX.XXX	
		Median	XXX.XX		XXX.XX		XXX.XX	
		Min, Max	XXX.X, XXX.X		XXX.X, XXX.X		XXX.X, XXX.X	
	Day 2	n	XXX	XXX	XXX	XXX	XXX	XXX
		Mean	XXX.XX	XXX.XX	XXX.XX	XXX.XX	XXX.XX	XXX.XX
		SD	XXX.XXX	XXX.XXX	XXX.XXX	XXX.XXX	XXX.XXX	XXX.XXX
		Median	XXX.XX	XXX.XX	XXX.XX	XXX.XX	XXX.XX	XXX.XX
		Min, Max	XXX.X, XXX.X	XXX.X, XXX.X	XXX.X, XXX.X	XXX.X, XXX.X	XXX.X, XXX.X	XXX.X, XXX.X

Etc...

[1] Baseline is defined as the latest available observation before drug administration.
 Data source: listings 16.x.x.x.x and 16.x.x.x.x.
 Source code: xxxx.ssc. Date/time of run: DDMMYYYY:HH:MM.
 Vital sign includes: blood pressure, heart rate

Page X of Y

Page 58 of 65

Effective date 01/08/2015

STA01form01v3

Advanced Accelerator Applications

Protocol: AAA-1002

Table 14.3.8.2 Vital Signs - Shifts from baseline
Population: Safety

Cohort: RA (N=xx)

Test (unit)	Visit	Result	Baseline Result				
			Low	Normal	High	Missing	Total
			n (%)	n (%)	n (%)	n (%)	n (%)
Systolic Blood Pressure Supine (xx/yy)	Day 2	Low	xx (xx.x)	xx (xx.x)	xx (xx.x)	xx (xx.x)	xx (xx.x)
		Normal	xx (xx.x)	xx (xx.x)	xx (xx.x)	xx (xx.x)	xx (xx.x)
		High	xx (xx.x)	xx (xx.x)	xx (xx.x)	xx (xx.x)	xx (xx.x)
		Missing	xx (xx.x)	xx (xx.x)	xx (xx.x)	xx (xx.x)	xx (xx.x)
		Total	xx (xx.x)	xx (xx.x)	xx (xx.x)	xx (xx.x)	xx (100)
	Day 30	Low	xx (xx.x)	xx (xx.x)	xx (xx.x)	xx (xx.x)	xx (xx.x)
		Normal	xx (xx.x)	xx (xx.x)	xx (xx.x)	xx (xx.x)	xx (xx.x)
		High	xx (xx.x)	xx (xx.x)	xx (xx.x)	xx (xx.x)	xx (xx.x)
		Missing	xx (xx.x)	xx (xx.x)	xx (xx.x)	xx (xx.x)	xx (xx.x)
		Total	xx (xx.x)	xx (xx.x)	xx (xx.x)	xx (xx.x)	xx (100)

Etc...

[1] Baseline is defined as the latest available observation before drug administration.

Percentages are based on the number of patients with at least one available baseline or post-baseline result.

[figure not shown]
Data source: listings 16.x.x.x.x and 16.x.x.x.x.

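### Laboratory and ECG extremes seen only at unscheduled or repeat tests reach no planned summary of those values: the SAP sends them to outputs that its table list does not contain

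*SAP*

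**What the plan says.** SAP 7.1.2 sets a rule in two parts. The first part excludes: "Data from unscheduled visits or repeat tests will not be used when descriptive statistics are presented by visit". The second part compensates: "all observed data including repeat tests and unscheduled visits will be presented in assessments of max and min changes on treatment, shift tables", and also in listings.

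The planned outputs are as follows.

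- **Laboratory.** SAP 7.9 describes statistics at each time point and adds "Summary statistics changes from baseline will also be presented". It mentions neither shift tables nor extremes. List 10.1 has Table 14.3.4.2, "Haematology parameters at each visit and change from baseline", with Tables 14.3.4.3 (biochemistry) and 14.3.4.4 (urinalysis) built the same way. It also has a subject-level output, Table 14.3.4.1, "Listing of Laboratory Safety Values for Subjects with Clinically Significant Abnormal Laboratory Values".
- **ECG.** Table 14.3.9.2, "Electrocardiogram parameters at each visit and change from baseline", Table 14.3.9.1 (interpretation, by visit in its shell), and a box plot of change from baseline (Figure 14.3.1).
- **Vital signs.** Table 14.3.8.1 by visit. SAP 7.11 also says "Number and percentage of subjects with shift changes from baseline will be tabulated in Shift Tables for each vital sign assessment", and Table 14.3.8.2, "Vital Signs - Shifts from baseline", delivers this.

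Protocol section 8 (Laboratory Tests) promises shift tables for every laboratory test, with classes below, within and above the normal range. SAP 7.19 states that the planned analysis has not changed.

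**The concern.** Keeping unscheduled and repeat results out of by-visit rows is sound practice, because such tests are often taken for cause and would distort a visit mean. It is safe only if another summary picks them up. SAP 7.1.2 recognises this and names the outputs that should do so, but for laboratory and ECG data those outputs are not in the plan.

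SAP 6.1 makes abnormal laboratory tests and changes in ECG parameters and vital signs primary safety endpoints. If the extremes found between visits are left out, the summarised ranges and largest changes can only look closer to normal than the data are.

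The schedule leaves room for this. Under protocol Table 1, a patient outside the sub-study has the first post-dose laboratory test at Day 30. After the second administration at Day 42, the next scheduled laboratory test and ECG are at Day 90. A transient abnormality in either gap would show only in an unscheduled test.

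**Working it through.** The plan gives no figure to reproduce. The check compares the rule in SAP 7.1.2 with the list of tables (10.1), the list of figures (10.2) and the shells (10.4).

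**Step 1: count the outputs that the rule relies on.** Among the laboratory, vital-sign and ECG outputs in list 10.1:

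- max/min-change or worst-value tables: 0
- shift tables: 1 (14.3.8.2, vital signs); laboratory 0, ECG 0
- tables whose titles say that they are by visit: 5 (14.3.4.2, 14.3.4.3, 14.3.4.4, 14.3.8.1, 14.3.9.2); Table 14.3.9.1 is also by visit in its shell

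**Step 2: follow one unscheduled value through each domain.**

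| Domain | By-visit summary | Max/min-change output | Shift table | Where the value appears |
|---|---|---|---|---|
| Laboratory | Excluded by 7.1.2 | Not planned | Not planned; promised in protocol section 8 | Subject listings; Table 14.3.4.1 if clinically significant; AE tables if reported as an event |
| ECG | Excluded by 7.1.2 | Not planned | Not planned | Subject listings; AE tables if clinically relevant |
| Vital signs | Excluded by 7.1.2 | Not planned | Planned (14.3.8.2) | Shift table by rule, but the shell gives it no place; subject listings |

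The text of the shell for the ECG box plot does not say which records are plotted. The general sentence in 7.1.2 limits summary statistics to scheduled visits, so the figure cannot be relied on to show the excluded values.

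**Step 3: read the vital-sign shell.** Table 14.3.8.2 shows Day 2 and Day 30 and is then abbreviated. It has no row for a post-baseline extreme. No section of the SAP says to which visit an unscheduled result belongs, or which result counts when a test is repeated. A programmer would have to invent the rule.

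**Step 4: measure the gaps between scheduled laboratory tests (nominal days).**

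- First dose to first laboratory test, outside the sub-study: 30 − 1 = 29 days.
- Second dose to next laboratory test: 90 − 42 = 48 days. With the ±14-day windows on both visits, this runs from (90 − 14) − (42 + 14) = 20 days to (90 + 14) − (42 − 14) = 76 days.

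**Step 5: try to size the effect.** This would need the number of unscheduled and repeat tests and how many of them exceeded the scheduled extremes. The documents give neither, so no magnitude can be calculated.

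**The case against.** The strongest reply is that nothing is lost. This is a single-arm study of about 20 patients with descriptive safety analysis, and every value is in the subject listings, with laboratory abnormalities flagged. Table 14.3.4.1 lists laboratory values for patients with clinically significant abnormalities, and nothing restricts it to scheduled visits. The protocol's adverse event definition covers abnormal laboratory findings, and its section 6 sends clinically relevant ECG abnormalities to the AE page. Such cases can therefore reach the TEAE tables, which report another primary safety endpoint.

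All of this stands, and it limits the seriousness of the point. It does not remove it. The AE tables and Table 14.3.4.1 depend on a judgement of relevance, and neither they nor the subject listings summarise the size of change across patients. None of them is the output that 7.1.2 says will exist.

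A reader might infer more than the documents support, in two ways.

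- **That the worst laboratory, vital-sign and ECG values reach no summary table at all.** A worst value at a scheduled visit enters the Min/Max rows of the by-visit tables. For vital signs, 7.1.2 assigns all observed data to shift tables and one is planned. An abbreviated shell without a worst-value row does not overrule that text; what is missing is the row or placement rule.
- **That one missed value moves an abnormality rate by 5 points (1/20), or by 10 in a disease group of 10 (1/10).** List 10.1 has no laboratory abnormality-rate table to which these figures could apply. They also use the planned numbers, although SAP 4.2 records that recruitment stopped early. Nor is every abnormality between visits missed, since one that persists is seen at the next visit.

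**Conclusion.** The point holds for laboratory and ECG values seen only at unscheduled or repeat tests. They are excluded from the by-visit tables and routed to outputs that are not planned, so they are missing from every planned summary of those values. The absent laboratory shift table is also an undeclared departure from protocol section 8, since SAP 7.19 reports no changes. For vital signs the defect is narrower: the shift table exists but does not say where such values go, and the max/min-change output is missing there too.

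The direction of any bias is towards normal. Its size is unknown and could be nil if no unscheduled or repeat test exceeded the scheduled extremes. The conclusion assumes that list 10.1 and the shells are the complete set of planned summaries and that 7.1.2 is followed as written. The correction is worth making because it carries out the SAP's own rule, on primary safety endpoints, at little cost.

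**What to change.** 1. Add 'minimum post-dose' and 'maximum post-dose' rows, each with value and change from baseline, to Tables 14.3.4.2 to 14.3.4.4 (numeric parameters), 14.3.8.1 and 14.3.9.2. Take them over all records after the first administration, including unscheduled and repeat tests.
2. Add the laboratory shift table promised in protocol section 8.
3. Give that table and Table 14.3.8.2 separate 'lowest post-dose' and 'highest post-dose' panels. A patient with both a low and a high value is then counted in each, and unscheduled and repeat values have a defined place.
4. Leave the by-visit rows unchanged, on scheduled visits only.
5. If the sponsor decides against the laboratory shift table, record that in SAP 7.19.

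The cost is one further table and some extra rows and panels in existing shells; no new data are needed. Worst-value rows will look less favourable than by-visit rows. Sub-study patients have one extra scheduled assessment at 24 hours and so one more chance of an extreme value, which a footnote should state.
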